### 1.5.2. Nonclinical Safety

PF-06840003 was assessed in a series of nonclinical studies with the oral route of exposure since this is the intended route of clinical administration. Good Laboratory Practice (GLP) 1-month repeat-dose studies were conducted in mice and dogs.

In the 1-month mouse study, the primary target organs were the CNS, liver, spleen, and adrenals. Four animals (2 main study, 2 toxicokinetic) receiving 2000 (1000 BID) mg/kg/day were euthanized prior to dosing on Day 2 due to PF-06840003 related adverse clinical signs, including decreased activity, partially closed eyes, recumbency, unable to rise, twitching, tremors and convulsions. No PF-06840003 related microscopic findings were observed in these animals, and therefore a cause for the morbidity was not determined. Dosing was discontinued after the second daily dose on Day 1 for this group of animals and resumed at 1200 (600 BID) mg/kg/day on Day 4. PF-06840003-related, non-adverse findings included microscopic findings in the liver (minimal to mild centrilobular hypertrophy associated with higher liver weight, and minimal increases in extra medullary hematopoiesis), spleen (increases in severity [mild and moderate] of extra medullary hematopoiesis associated with higher splenic weight), adrenals (increases in severity [mild] of vacuolated cells in the X zone in female mice only), increased adrenal weight (male mice only), higher cholesterol (female mice only), and higher globulin values with lower associated albumin/globulin ratios (female mice only). Additional PF 06840003-related, non-adverse findings included intermittent observation of discolored urine without associated microscopic changes, and higher body weight and food consumption. All changes showed reversibility at the end of the 1-month recovery phase.

In the 1-month dog study, the primary target organs or systems were the liver, thyroid, and the cardiovascular, hematopoietic, and coagulation systems. PF-06840003 related, adverse microscopic findings were noted in the liver (minimal to mild hepatocellular degeneration with accompanying increases in hepatic enzymes [1.4 19x baseline] and/or serum and urine bilirubin [2-4x baseline]); adverse effects on body weight and food consumption with associated adverse clinical signs were also noted. Additional non-adverse liver effects included decreased glycogen content of hepatocytes considered secondary to decreased food consumption, higher liver weights without microscopic correlates, and deposition of pigmented material (hemosiderin) in Kupffer cells related to the primary finding of mild hepatocellular degeneration and associated hemorrhage. PF-06840003-related, non-adverse effects were observed in the thyroid (minimal follicular cell hypertrophy) and thymus (minimal decrease in lymphoid cellularity, lower thymus weight). The changes noted in the thymus were observed in a single high dose (600 [300 BID] mg/kg/day) male dog showing adverse clinical signs and were considered secondary to stress. PF-06840003-related, non-adverse effects were also observed in clinical pathology parameters (decreased red cell mass parameters and albumin, increased prothrombin time, activated partial thromboplastin time and fibrinogen). Additional PF-06840003-related, non-adverse changes included emesis, abnormal urine color and lower urine pH. All changes showed reversibility at the end of the 1-month recovery phase, except for the deposition of hemosiderin in Kupffer cells and the change in prothrombin time. Reversibility of the effects on prothrombin time could not be evaluated as recovery animals did not demonstrate these changes during the dosing phase, but would be expected to recover based on the normalization of activated partial thromboplastin time during recovery.

## 1.6. Starting Dose Rationale

The selection of the starting dose for this first-in-patient (FIP) study is based on the preclinical toxicology results in accordance with the International Conference on Harmonization (ICH) S9 Guidance entitled “Nonclinical Evaluation for Anticancer Pharmaceuticals”, as well as predicted pharmacologically active dose in humans. Results from preclinical toxicity studies indicate that mouse is the most sensitive species, and STD10 in mouse was determined to be 1200 mg/kg. Based on S9 guidance, the STD10 of 1200 mg/kg in mouse results in Maximum Recommended Starting Dose (MRSD) of approximately 580 mg in human (assuming body weight of 60 kg), which is greater than the projected human pharmacological active dose ranging from 125 to 500 mg derived from IDO1 inhibition. Therefore, the recommended starting dose for this FIP study is 125 mg given as oral administration once daily (QD), and this dose represents approximately 1/47th of mouse STD10 (based on human equivalent dose normalized to body surface area). In addition, given the projected human PK parameters, the projected human AUC for PF-06840003 at the proposed starting dose of 125 mg is expected to be approximately 1/18th of the observed mouse AUC at STD10.

Complete information for this compound may be found in the single reference safety document (SRSD), which for this study is the investigator’s brochure.

## 2. STUDY OBJECTIVES AND ENDPOINTS

### 2.1. Objectives

#### Primary Objective – Part 1

- To evaluate the safety and tolerability of increasing dose levels of daily oral PF-6840003 in patients with malignant gliomas.
- To characterize the dose limiting toxicities (DLTs) of escalated doses of PF-06840003.
- To determine the maximum tolerated dose (MTD) or recommended phase 2 dose (RP2D).

#### Primary Objective – Part 2

- To further evaluate the safety and tolerability of PF-06840003 at the RP2D.
- To evaluate the efficacy of PF-06840003 in patients with glioblastoma.

## Secondary Objectives – Parts 1 and 2

- To evaluate the overall safety profile.
- To characterize the single and multiple dose plasma PK of active enantiomer PF-06840002, and inactive enantiomer PF-06840001 after administration of the racemic mixture, PF-06840003.
- To document any anti-tumor activity (Part 1 only).
- To evaluate dose and concentration response relationship for target engagement and PD biomarkers and to then correlate with PK, safety and efficacy to select dose with full or optimal target engagement.
- To assess the CSF PK exposure of active enantiomer PF-06840002, and inactive enantiomer PF-06840001 after administration of the racemic mixture, PF-06840003.

CCI [REDACTED]

- [REDACTED]
- [REDACTED]
- [REDACTED]
- [REDACTED]
- [REDACTED]
- [REDACTED]
- [REDACTED]
- [REDACTED]

## 2.2. Endpoints

### Primary Endpoint – Part 1

- Incidence and grade of treatment-emergent adverse events (TEAE) including DLTs as graded by National Cancer Institute Common Terminology Criteria for Adverse Events (CTCAE) version 4.03.

## Primary Endpoints – Part 2

- Adverse Events (AE) as characterized by type, frequency, severity, timing, seriousness, and relationship to study therapy.
- Disease control rate (DCR) at 9 and 25 weeks by MRI using Macdonald criteria (Macdonald et al, 1990).

## Secondary Endpoints

- Laboratory abnormalities as characterized by type, frequency, severity (as graded by NCI CTCAE v.4.03) and timing;
- Vital Signs;
- PK parameters in the blood of PF-06840002 and PF-06840001 Single Dose (SD) –  $C_{max}$ ,  $T_{max}$ ,  $AUC_{last}$ ,  $AUC_{\tau}$ ,  $CL/F$ , and  $V_z/F$  and  $t_{1/2}$ ,  $AUC_{inf}$  as data permit. Multiple Dose (MD) (assuming steady state is achieved) –  $C_{ss,max}$ ,  $T_{ss,max}$ ,  $AUC_{ss,\tau}$ ,  $t_{1/2}$ ,  $C_{ss,min}$ ,  $C_{ss,av}$ ,  $CL/F$ ,  $V_{ss}/F$ ,  $R_{ac}$  ( $AUC_{ss,\tau}/AUC_{sd,\tau}$ ) and  $R_{ss}$  ( $AUC_{ss,\tau}/AUC_{sd,inf}$ ) as data permit;
- Objective tumor response based on Macdonald criteria.
- Disease Control Rate at 9 and 25 weeks by MRI based on Response Assessment for Neuro-Oncology (RANO) criteria.
- On-target activity of PF-06840003 by measurement of kynurenine, tryptophan and kyn/trp (ratio) levels in peripheral blood.
- Steady-state trough level ratio between CSF and plasma samples for PF-06840002 and PF-06840001.

CCI [REDACTED]

CC [REDACTED]  
[REDACTED]  
[REDACTED]  
[REDACTED]  
[REDACTED]  
[REDACTED]

**C**  
**C**  
**I**

[REDACTED]

[REDACTED]

[REDACTED]

### 3. STUDY DESIGN

#### 3.1. Study Overview

[figure not shown]
This is a Phase 1, open-label, multi-center, multiple-dose, safety, PK and PD study of single agent PF-06840003. This study contains two parts, dose escalation (Part 1) followed by dose expansion (Part 2). In Part 1, sequential cohorts of patients with recurrent malignant gliomas (GBM and/or WHO grade III anaplastic gliomas) will receive escalating doses of PF-06840003. Part 2 will evaluate safety as well as explore preliminary antitumor activity of the dose selected from Part 1 in additional patients with GBM.

The actual number of patients enrolled in the study will depend on the tolerability of PF-06840003 and the number of dose levels required to identify the MTD or Recommended Phase 2 Dose (RP2D) if the MTD is not reached. The target sample size for each cohort in Part 1 is 2-4 patients, but, the actual number of patients treated at each dose will vary from 2 to 12. It is estimated that the maximum sample size will be approximately 72 patients in Part 1 of the study, although this may be higher if more than 6 dose levels are required to be evaluated. Up to approximately 20 to 25 patients are anticipated to be enrolled in Part 2 of the study.

PF-06840003 will be administered daily as an oral dose in 28 day cycles with a starting dose of 125 mg once daily (QD). The pre-specified nominal doses for use in the dose escalation are 125 mg/day, 250 mg/day and 500 mg/day of PF-06840003. If the MTD or RP2D are not reached within the pre-planned nominal dose range, and the PK and PD data show that the target coverage is not optimal, the sponsor, in conjunction with the investigators, after careful consideration of all available safety, laboratory and PK information may expand the nominal dose range to a higher dosage, up to a maximum dosage of 1000 mg per day. Based on emerging clinical and PK data, twice a day (BID) dosing may be explored. For example, if the exposure over 24 hours does not allow for sufficient target coverage it may be determined that BID dosing is needed. In such a case, BID dosing will be initiated at the QD dose level where no DLTs are observed (ie, starting dose of BID dosing will be 250 mg BID after safety and tolerability profile of 250 mg QD is confirmed). Once a BID dosing regimen is initiated for further escalation towards the MTD, the escalation with a QD regimen will be suspended. Intermediate doses may also be used if required.

The overall study design is depicted in Figure 2. Treatment will continue until either disease progression, patient refusal, or unacceptable toxicity occurs, whichever is earliest, unless the investigator and medical monitor agree to treatment beyond disease progression based on individual benefit/risk assessments.

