10. **Pregnancy Test:** For female patients of childbearing potential, a serum or urine pregnancy test, with sensitivity of at least 25 mIU/mL and assayed in a certified laboratory, will be performed on two occasions prior to starting study treatment – once at the start of screening and once on C1D1 immediately before investigational product administration. Pregnancy tests will also be routinely repeated at every cycle during the active treatment period, at the end of study treatment and additional whenever one menstrual cycle is missed or when potential pregnancy is otherwise suspected. Additional pregnancy tests may also be undertaken if requested by institutional review board (IRB) or if required by local regulations.
11. **Registration:** Patient number and dose level allocation provided by Pfizer Inc. Registration should occur before any other Day 1 activities are performed and preferably no more than 3 business days before Day 1.
12. **Study Treatment:** Daily oral dosing with PF-06840003 will be initiated on Cycle 1 Day 1 and should continue until end of treatment. Patients assigned to a BID dosing regimen should be instructed to take PF-06840003 every 12 hours ( $\pm$ 1 hour). On days when patients have clinic visits where PK assessments are to be obtained, PF-06840003 should be held (NOT taken) prior to the study visit. The PF-06840003 can be taken after the study procedures required for that visit have been performed.

13. **Inpatient Evaluation for PK Assessment:** For cohorts where 500 mg QD or 500 mg BID or higher will be evaluated, patients will be required to undergo inpatient evaluation for at least 24 hours following receipt of the Cycle 1 Day 1 and Cycle 1 Day 15 dose. The evaluation will be used for collection of samples for evaluation of the PF-06840003 pharmacokinetics.

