### 3.1.1. Criteria for Dose Escalation

In Part 1 of the study, dose escalation and de-escalation will follow a modified Toxicity Probability Interval (mTPI) method, targeting a DLT rate of 27.5% and an acceptable DLT interval 22.5 to 32.5%. The dose levels to be evaluated in Part 1 of the study are listed in the following table:

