**Table 1. Dose Escalation Potential Dose Levels**

| Potential Dose Level | PF-06840003 (mg QD)*  | PF-06840003 (mg BID)  |
|----------------------|---|---|
| Starting Dose        | 125   | N/A   |
| 2                    | 250   | N/A   |
| 3                    | 500   | 250   |
| 4                    | 750   | 500   |
| 5                    | 1000  | 750   |
| 6                    | To be determined  | 1000  |
| 7                    | Escalation to continue to the MTD or desired pharmacological activity | Escalation to continue to MTD or desired pharmacological activity |

\* While a more frequent dosing regimen is initiated for further escalation towards the MTD, the escalation with a QD regimen will be suspended.

The mTPI method relies upon a statistical probability algorithm, calculated using all patients treated in the current dose level to determine one of the following dose-finding decisions: the subsequent dose should be escalated, maintained at the current dose, or de-escalated in the next cohort of 2 to 4 patients, or the trial should be terminated.

As an example, if the total number of patients treated at the current dose level is 4, the following dosing rules are applied:

- 0 DLT -> escalate
- 1 DLT -> remain at the same dose
- 2 DLTs -> de-escalate
- 3-4 DLTs -> de-escalate and consider current dose as intolerable

The general approach to dose-finding, using the mTPI method, involves the following:

- The target cohort size is 2 to 4, depending on the number of potential patients identified at participating sites;
- The next cohort can be enrolled when all patients at the current dose cohort have been evaluated for 28 days of the first treatment cycle, or experience a dose-limiting toxicity (DLT), whichever comes first;
- If a patient withdraws from the study before receiving  $\geq 80\%$  of the planned first-cycle dose for reasons other than investigational product-related toxicity, another patient will be enrolled to replace that patient at the current dose combination;
- In the situation in which the safety of the starting dose does not allow for escalation to the next dose level, a lower dose will be considered.

The dose escalation portion of the study is completed when at least 6 to 12 evaluable patients have been treated at the highest dose associated with DLT rate  $\leq 32.5\%$ .

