## **9.2. Statistical Methods and Properties**

### **9.2.1. Statistical Methods for Dose Escalation/De-Escalation**

Part 1, the dose escalation phase of this study, employs an mTPI design to estimate the MTD. The mTPI design employs a simple beta binomial model with a conjugated prior beta (0.5, 0.5). Decision rules are based on calculating the unit probability mass (UPM) of 3 intervals corresponding to underdosing, proper dosing, and overdosing in terms of dose limiting toxicity. A proper dosing interval is centered at the target toxicity rate (pT) of 27.5% with 5% uncertainty ( $0.225 < pT < 0.325$ ). The under dosing interval is (0, 0.225), and the overdosing interval is (0.325, 1). The 3 dosing intervals are associated with 3 different dose escalation decisions. The underdosing interval corresponds to a dose escalation I, overdosing corresponds to a dose de-escalation, and proper dosing corresponds to staying at the same current dose. Given an interval and a probability distribution, the UPM of that interval is defined as the probability of the interval divided by the length of the interval. The mTPI design calculates the UPMs for the 3 dosing intervals, and the one with the largest UPM implies the corresponding dose finding decision. That decision provides the dose level to be used for future patients. For example, if the underdosing interval has the largest UPM, decision E (to escalate) will be executed, and the next cohort of patients will be treated at the next higher dose level. Under the mTPI design, a trial is terminated when either the lowest dose is above the MTD or a pre-specified maximum sample size is reached. Doses with an incidence of DLT >33% (eg, 4 out of 10) will not be declared as MTD even though it is allowed by the mTPI method.

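### The protocol text caps the dose range at 1000 mg per day without limiting that to once-daily dosing, but Table 1 lists potential BID levels of 1500 and 2000 mg/day, and no visible text says which limit holds

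*Protocol*

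**What the plan says.** Protocol Section 3.1 gives the nominal doses as daily amounts: 125, 250 and 500 mg/day. If neither the MTD nor the RP2D is reached in that range and target coverage is not optimal, the sponsor, with the investigators, "may expand the nominal dose range to a higher dosage, up to a maximum dosage of 1000 mg per day". The Protocol Summary (Study Treatment) repeats this. The sentences that follow allow BID dosing from 250 mg BID and state no BID maximum.

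Section 3.1.1 then says: "The dose levels to be evaluated in Part 1 of the study are listed in the following table". That table is Table 1, headed as potential dose levels. Its QD column runs 125, 250, 500, 750 and 1000 mg. Its BID column starts at level 3 and runs 250, 500, 750 and 1000 mg. The level 6 row reads "To be determined | 1000", QD first and BID second. Level 7 is "Escalation to continue to the MTD or desired pharmacological activity" for QD and "Escalation to continue to MTD or desired pharmacological activity" for BID.

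Section 9.2.1 says that on a decision to escalate "the next cohort of patients will be treated at the next higher dose level", and that "a trial is terminated when either the lowest dose is above the MTD or a pre-specified maximum sample size is reached". It mentions no maximum dose. SAP Sections 4.2 and 8.1 restate the escalation rules and also give no dose ceiling.

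**The concern.** The only maximum dose in the text of this first-in-patient study does not fit its own escalation table. The nominal doses just before it are daily amounts, so the natural reading of the cap is total daily dose. On that reading, two listed BID levels lie above the limit.

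An investigator or ethics committee cannot tell from the protocol whether a dose above 1000 mg/day is permitted. The answer could also affect the MTD. Section 3.3 defines it as the highest dose actually tested whose DLT rate is at most 32.5%, so it depends on how far testing may go.

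**Working it through.** **1. The stated figure.** The cap is 1000 mg per day (Section 3.1 and Protocol Summary). The QD column agrees with it: the highest numeric QD level is 1000 mg × 1 = 1000 mg/day. The unspecified QD level 6 and the open level 7 come after that.

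**2. The BID column.** Daily dose = 2 × the dose in Table 1.

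| BID level | mg/day | Ratio to 1000 mg/day |
|---|---|---|
| 250 mg | 2 × 250 = 500 | 0.5 |
| 500 mg | 2 × 500 = 1000 | 1.0 |
| 750 mg | 2 × 750 = 1500 | 1.5 |
| 1000 mg | 2 × 1000 = 2000 | 2.0 |

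Two of the four numeric BID levels exceed the cap. The highest listed BID level within it is 500 mg.

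**3. Length of the BID path.** With BID starting at 250 mg after 250 mg QD (Section 3.1), Table 1 gives six numeric levels: 125 and 250 mg QD, then 250, 500, 750 and 1000 mg BID. Under a 1000 mg/day cap there are four. Intermediate doses could add to either count.

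**4. Whether the rules can reach the conflict.** Table 2 marks E (escalate) in 11 cells with 0 DLTs (n = 2 to 12), 8 cells with 1 DLT (n = 5 to 12) and 2 cells with 2 DLTs (n = 11 and 12). That is 11 + 8 + 2 = 21. I recomputed each decision from Section 9.2.1: posterior beta(0.5 + DLTs, 0.5 + n − DLTs), with unit probability mass = interval probability ÷ interval length for (0, 0.225), (0.225, 0.325) and (0.325, 1). For 0 DLTs in 4 patients:

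- under-dosing: 0.860 / 0.225 = 3.82
- proper dosing: (0.933 − 0.860) / 0.1 = 0.73
- over-dosing: (1 − 0.933) / 0.675 = 0.10

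The largest is under-dosing, so the decision is E. All 21 cells reproduce as E, and no other cell does. Any of them at 500 mg BID points to 750 mg BID. The count shows that the conflict can be reached. It does not say how likely that is.

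**5. How far the trigger is from the expected dose.** Section 1.5.1 projects the active dose as 200 mg BID (2 × 200 = 400 mg/day) or 500 mg QD. The cap is 1000/400 = 2.5 or 1000/500 = 2.0 times that. Coverage would have to be judged insufficient at 2.0 to 2.5 times the projected active daily dose.

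**The case against.** The strongest reply is that the cap was meant for QD dosing only. It stands before the BID sentences, refers to extending the nominal range, and equals the highest numeric QD level. The Document History records that Amendment 1 added BID dosing, and Sections 3.1 and 9.3 allow for more than six dose levels. Footnote 13 of the Schedule of Activities begins "For cohorts where 500 mg QD or 500 mg BID or higher will be evaluated", and Section 7.4.1 uses a similar phrase, so BID doses above 500 mg seem to have been contemplated. All this makes a drafting omission the likeliest explanation. It does not settle the matter, because no visible text limits the cap to QD. That reading would also leave BID with no numeric ceiling in the text, and QD levels 6 and 7 would still be in tension with the cap.

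Three further points reduce the weight of the conflict:

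- Table 1 lists potential levels, and the text under Figure 2 says that doses may be reconsidered and amended. A reader might infer that the protocol commits to dosing at 2000 mg/day. It does not. Still, neither text says which limit holds.
- A reader might infer that the algorithm compels a dose above the cap. It does not. Expansion is at the discretion of the sponsor and investigators after review of safety, laboratory and PK data, and Section 9.8 adds continuing review.
- A reader might infer that sites could dose by the wrong text. Section 5.1 has the sponsor specify each patient's dose level in writing, so sites do not choose.

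Figure 2 is not reproduced in the text available, so whether it states a limit could not be checked.

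**Conclusion.** The inconsistency is real and should be corrected. As worded, the cap excludes 750 and 1000 mg BID, which Table 1 lists at 1.5 and 2.0 times that cap, and nothing visible in the protocol or SAP reconciles the two.

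Its reach is narrow. It has no effect if escalation stops at or below 1000 mg/day, which is plausible given the projected active dose. If escalation goes further, the governing text decides whether higher levels may be tested and could therefore affect the estimated MTD. The effect on the RP2D is less direct, because Section 3.5 allows it to be set below the MTD.

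This point does not show that doses above 1000 mg/day are unsafe, or that either limit is the wrong one. The conclusion rests on reading the cap as total daily dose, as its wording and the preceding nominal doses suggest, and on Figure 2 giving no limit.

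**What to change.** In the Protocol Summary and Section 3.1, state one maximum total daily dose, or separate QD and BID maxima, and make Table 1 match:

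- If 1000 mg/day is the limit, end Table 1 at 1000 mg QD and 500 mg BID.
- If the higher BID levels are intended, state maxima of 1000 mg QD and 1000 mg BID (2000 mg/day), with a short safety justification.
- In both cases, remove QD level 6 and level 7 or give them numeric limits.

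Add to Section 9.2.1 that escalation stops at the ceiling. If the decision there is still E, the MTD is reported as not reached and the RP2D is chosen at or below the ceiling. That condition is needed because a ceiling dose with a DLT rate in or near the target interval could itself be the MTD under Section 3.3. Section 3.1 already foresees an RP2D without an MTD, so the addition only ties that outcome to the ceiling.

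The cost is amendment wording, plus the justification if the higher limit is kept. Table 2 and the analyses stay as they are. If 1000 mg/day is kept, higher doses go untested and the MTD may not be reached. The choice of maximum belongs to the sponsor and investigators.
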